## **7.5 Measurements of Treatment Compliance**

Not applicable.

## 7.6 Efficacy

Analysis of the primary, key secondary and other time-to-event efficacy endpoints will be performed in the ITT population. Other secondary efficacy endpoints will be based on the FAS population. A sensitivity analysis will be performed for the primary endpoint, key secondary and other time-to-event efficacy endpoints in the FAS population. Supportive analyses of the primary and key secondary efficacy endpoint will be performed on the PP population.

In all analyses (ITT, FAS and PP), the correct value of the stratification strata as derived using the Charlson comorbidity index and the pre-baseline Barthel index

data collected in the eCRF will be used instead of the investigator-derived value from IRT.

#### 7.6.1 Primary Efficacy Analysis

Time to sustained withdrawal of oxygen supplementation (in days) with no subsequent reutilisation during remaining study period is defined as the first day, from randomisation through completion of the study, on which a patient

- i. satisfies categories 0 to 4 on the 11-point WHO Clinical Progression Scale, and
- ii. has no subsequent reutilisation of oxygen supplementation (5 to 10 on the 11-point WHO Clinical Progression Scale)

Patients who reported sustained withdrawal of oxygen supplementation will be considered as an event on the date when patient meets categories 0 to 4 on the 11-point WHO Clinical Progression Scale and has no subsequent reutilisation of oxygen supplementation. Otherwise, in case of early study discontinuation due to any reason the patient will be censored at the date of the early study discontinuation. Otherwise, the patient will be censored at the date of the Day 31 visit or death date, whichever is first. If the patient was lost to follow-up between day 15 and day 31 visit, and there is an attempt of contact and study discontinuation on or after the day 31 visit due date, the patient will be censored at day 31.

Time-to sustained withdrawal of oxygen supplementation (days) = (date of event or censoring – date of randomisation)

If date of event is the same as the randomisation date then time-to sustained withdrawal of oxygen supplementation will be considered as 1 day. If no data is available then time will be censored at time 0.

Time-to sustained withdrawal of oxygen supplementation will be analysed using the Kaplan-Meier method and 25th percentile, median and 75th percentile time will be presented by treatment group together with 95% CIs. The 95% CIs will be computed based on Brookmeyer-Crowley method and using a log log transformation. The mean time to sustained withdrawal of oxygen supplementation and its standard error will be also presented by treatment group.

Time-to sustained withdrawal of oxygen supplementation between each dose of plitidepsin versus control arm will be compared using a stratified log-rank test, including the randomisation stratification factors as covariates, ie, Geographical Region (Europe vs. Rest of the World), Charlson Comorbidity index (0-1 vs. >1) and pre-baseline Barthel index ( $\geq$ 90 versus <90) as derived using the eCRF data. The 2-sided p-values for the comparison of each dose of plitidepsin versus control arm will be presented.

The 2-sided p-values from the stratified log-rank test will be adjusted for multiplicity using the Hochberg step-up procedure to preserve the type 1 error rate in the comparison of each dose of plitidepsin versus control arm. The Hochberg

step-up procedure will be implemented as following: • Let  $p_1 \leq p_2$  denote the ordered unadjusted 2-sided p-values with associated null hypotheses  $H_{01}$  and  $H_{02}$ , where  $H_{0i}$  = time to sustained withdrawal of oxygen supplementation in plitidepsin [1.5 mg or 2.5 mg] arm = time to sustained withdrawal of oxygen supplementation in control arm.

- Then we follow the next stepwise procedure:
  - If  $p_2 \leq 0.05$ , reject  $H_{01}$  and  $H_{02}$  stop; else continue
  - If  $p_1 \leq 0.05/2$ , reject  $H_{01}$  and stop
- Adjusted 2-sided p-values will be calculated as:
  - $\circ q_2 = p_2$
  - $\circ q_1 = \min[2^* p_1, q_2]$

The adjusted 2-sided p-values for multiplicity using the Hochberg step-up procedure will be also presented.

As supportive analyses:

- A stratified Cox proportional-hazards regression model, including the randomisation stratification factors as covariates, ie, Geographical Region (Europe vs. Rest of the World), Charlson Comorbidity index (0-1 vs. >1) and pre-baseline Barthel index ( $\geq$ 90 versus <90) as derived using the eCRF data, will be applied to compare results between each dose of plitidepsin versus control arm. Hazard ratios, 95% CIs, and 2-sided p-values for the comparison of each dose of plitidepsin versus control arm will be presented.
- A Bootstrap analysis simulating the original sample size (n=203 per treatment group) will be implemented with the actual sample size in order to investigate what would have been the variability of the observed hazard ratio and the confidence interval if the trial's recruitment would not be stopped. Bootstrap resamples simulating the original sample size (n=203 per)treatment group, n=609 in total and 10000 replications) will be created and a stratified Cox proportional-hazards regression model, including the fixed effect of the treatment group will be applied to compare results between each dose of plitidepsin versus control arm. The median value of the hazard ratios, the corresponding 95% CIs calculated as the 2.5% and 97.5% percentiles of the hazard ratios, and the median of the 2-sided p-values for the comparison of each dose of plitidepsin versus control arm will be presented. In addition, the percentage of samples with Hazard Ratio > 1 and the percentage of samples with 2-sided p-value < 0.025 will be also shown.

CONFIDENTIAL

- The inconsistencies between the 11-point WHO Clinical Progression Scale and the oxygen supplementation status will be incorporated in an extended definition of the primary efficacy endpoint, i.e., time to sustained withdrawal of oxygen supplementation (in days) with no subsequent reutilisation during remaining study period is defined as the first day, from randomisation through completion of the study, on which a patient
  - i. satisfies categories 0 to 4 on the 11-point WHO Clinical Progression Scale or 'No supplemental oxygen needed' is recorded in the 'Vital Sign Oxygen status' form, and
  - has no subsequent reutilisation of oxygen supplementation (5 to 10 on the 11-point WHO Clinical Progression Scale or any oxygen supplementation is recorded in the 'Vital Sign Oxygen status' form)

The cumulative proportion of sustained withdrawal of oxygen supplementation (1cumulative survival) will be displayed graphically by treatment group using a Kaplan-Meier curve.

The primary efficacy analysis described above will be performed using the ITT population. A sensitivity analysis using the same model will be performed in the FAS population and a supportive analysis using the same model will be performed using the PP population.

If the accrual in any of the experimental arm is stopped after the interim analysis, the final analysis for the primary endpoint in the remaining arms will be performed at the 1.25% (1-sided) or 2.5% (2-sided) level using a Bonferroni-adjusted type I error rate.

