#### CONFIDENTIAL

\*Body weight and height should be measured at screening.

- 1 Informed consent: Must be obtained before the patient undergoes any study-specific procedure
- 2 Selection criteria: Confirm that patient meets all inclusion criteria and none of the exclusion criteria
- 3 Vital signs: Temperature, sitting blood pressure, heart rate, respiratory rate, PaO2 (obtained either by arterial blood gas analyses or from saturation of oxygen (SpO2) by pulse oximetry, and its respective FiO2 to be measured at screening, on Days 1 to 3 just before start and end of each plitidepsin infusion (plitidepsin groups)/once daily on Days 1 to 3 (control group), further once daily while the patient is hospitalised, and on Days 8, and 31 (±3 days). To estimate the PaO2/FiO2 ratio, the required equation would be used for imputing PaO2 from SpO2, and the information on the oxygen delivery devices and oxygen flow prescribed would be utilised for imputation of FiO2.
- 4 ECG: QTcF prolongation to be assessed at screening and on Days 1, 3 (postinfusion), and 31 (±3 days), and any QTcF values >500 msec will be flagged as increasing the likelihood of the treatment being proarrhythmic (per ICH Guidance E14)
- 5 Haematology: RBC, haemoglobin, haematocrit, WBC with differential, platelet count. Testing to be performed by the local laboratory for screening and by central laboratory for on-study tests (tests performed within 24 hours of screening do not have to be repeated)

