- 13 Clinical Status: Assessed using the 11-point WHO Clinical Progression Scale will be performed at screening, daily from Day 1 while hospitalised and on Days 8 (±1 day), 15 (±1 day), and 31 (±3 days), where 0= uninfected, no viral RNA detected; 1 = asymptomatic, viral RNA detected; 2 = symptomatic, independent; 3 = symptomatic, assistance needed; 4 = hospitalised, no oxygen therapy (if hospitalised for isolation only, record status as for ambulatory patient); 5 = hospitalised, oxygen by mask or nasal prongs; 6 = hospitalised, oxygen by NIV or high flow; 7 = intubation and mechanical ventilation, pO2/FIO2 ≥ 150 or SpO2/FIO2 ≥ 200; 8 = mechanical ventilation, pO2/FIO2 < 150 and vasopressors, dialysis or ECMO; 10 = dead.

- 14 Functional Status: Assessed by the Barthel index score (Appendix 3); the pre-baseline (ie, > 1 month prior to at screening) functional status should be recorded, in addition to Day 1 prior to initiating study treatment, at hospital discharge, and on Days 8 (±1 day), 15 (±1 day), and 31 (±3 days).

CONFIDENTIAL

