# Table 14.2.1.1.5 Time to Sustained Withdrawal of Oxygen Supplementation - Adding Oxygen Supplementation Status Analysis (Intent-To-Treat Population)

Variable	Plitidepsin 2.5mg (N=XXX)	Plitidepsin 1.5mg (N=XXX)	Control Arm (N=XXX)
Supportive Analysis – Adding Oxygen Supplementation Status			
Patients who Reported Sustained Withdrawal of Oxygen			
Supplementation, n (%)	xxx (xx.x)	xxx (xx.x)	xxx (xx.x)
Censored Patients, n (%)	xxx (xx.x)	xxx (xx.x)	xxx (xx.x)
Time-to Sustained Withdrawal of Oxygen Supplementation (days)			
25th percentile	xx.x (xx.x. xx.x)	xx.x (xx.x. xx.x)	xx.x (xx.x. xx.x)
Median	xx.x (xx.x. xx.x)	xx.x (xx.x. xx.x)	xx.x (xx.x. xx.x)
75th percentile	xx.x (xx.x, xx.x)	xx.x (xx.x, xx.x)	xx.x (xx.x, xx.x)
Mean (SE)	xx.x (xx.x)	xx.x (xx.x)	xx.x (xx.x)
Stratified Log-Rank Test			
2-sided p-value [b]	X.XXX	X.XXX	
2-sided p-value adjusted for Multiplicity [b,c]	X.XXX	X.XXX	
Supportive Analysis - Stratified Cox Regression Model			
Hazard Ratio [d,e]	X.XXX	X.XXX	
95% CI for Hazard Ratio [d,e]	x.xxx - x.xxx	X.XXX - X.XXX	
2-sided p-value [d]	X.XXX	X.XXX	

N = number of patients in analysis set. % = percentages are calculated based on N as the denominator.

CI = Confidence interval; SE = Standard Error.

Notes: Sustained withdrawal of oxygen supplementation (in days) with no subsequent reutilisation during remaining study period is defined as the first day, from randomisation through completion of the study, on which a patient

i. satisfies categories 0 to 4 on the 11-point WHO Clinical Progression Scale or 'No supplemental oxygen needed' is recorded in the 'Vital Sign Oxygen status' form, and

ii. has no subsequent reutilisation of oxygen supplementation (5 to 10 on the 11-point WHO Clinical Progression Scale or any oxygen supplementation is recorded in the 'Vital Sign Oxygen status' form)

[a] Calculated using the Kaplan-Meier estimator. CIs derived based on Brookmeyer-Crowley method and using a log log transformation.

[b] 2-sided p-values calculated using a stratified log-rank test, including the fixed effect of the treatment group and levels of the randomisation stratification factors, ie, geographical region (Europe vs. Rest of the World), Charlson Comorbidity Index (0-1 vs. >1) and pre-baseline Barthel index ( $\geq$ 90 versus <90) as derived using the eCRF data as covariates.

[c] Stratified log-rank test p-values adjusted for multiplicity using the Hochberg step-up procedure.

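### In the supportive extended definition of oxygen withdrawal, a day on which the WHO scale and the oxygen form disagree can count as the event while one source still records oxygen

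*SAP*

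**What the plan says.** The primary definition in SAP section 7.6.1 uses the WHO scale alone. A patient "will be considered as an event on the date when patient meets categories 0 to 4 on the 11-point WHO Clinical Progression Scale", provided there is no later return to categories 5–10. A patient without an event who did not leave the study early is handled as follows: "the patient will be censored at the date of the Day 31 visit or death date, whichever is first".

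The same section adds a supportive version: "The inconsistencies between the 11-point WHO Clinical Progression Scale and the oxygen supplementation status will be incorporated in an extended definition". The shell of Table 14.2.1.1.5 repeats it. Criterion (i) is met on the first day on which the patient "satisfies categories 0 to 4 on the 11-point WHO Clinical Progression Scale or 'No supplemental oxygen needed' is recorded in the" oxygen-status form. Criterion (ii) begins "has no subsequent reutilisation of oxygen supplementation (5 to 10 on the" WHO scale, and is widened to "Progression Scale or any oxygen supplementation is recorded in the 'Vital Sign Oxygen status' form". Both criteria therefore join the two sources with 'or', and criterion (ii) is limited to subsequent use.

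The extended definition has no rule for a day on which the sources disagree, and none for a last visit after which no record is subsequent.

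**The concern.** The definition exists to deal with records in which the scale and the form disagree, and those are the only records on which its two criteria conflict. If either source is enough to show withdrawal, and either is enough to show use but only later, a discordant day passes as withdrawal without being checked for use.

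Such records are plausible. WHO categories 5 and 6 are worded for hospitalised patients, so a discharged patient still on oxygen could be scored 2 or 3 while the form records oxygen.

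Table 14.2.1.1.5 reports event counts, log-rank p-values with Hochberg adjustment, and hazard ratios from this definition. A patient with oxygen recorded in one source at the final visit would be counted in that table as withdrawn.

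**Working it through.** No figure in the SAP depends on this definition, so there is none to reproduce. The check is one of logic.

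**Inputs.** Criteria (i) and (ii) come from section 7.6.1 and the Table 14.2.1.1.5 shell. The event-date and censoring rules come from the primary definition and are assumed to carry over. The assessment schedule comes from the Appendix 4 footnotes. The WHO scale is scored "daily from Day 1 while hospitalised and on Days 8 (±1 day), 15 (±1 day), and 31 (±3 days". Vital signs, whose schedule the oxygen form is taken to follow, are measured "further once daily while the patient is hospitalised, and on Days 8, and 31 (±3 days". Both sources can therefore be present, and disagree, at Day 31.

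**Step 1: are the criteria complements?** In the primary definition they are: a day is WHO 0–4 or WHO 5–10, never both. Looking only forward in (ii) is then safe. In the extended definition:

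| WHO score | Form | Meets (i) | Counts as oxygen use in (ii) |
|---|---|---|---|
| 0–4 | none | yes | no |
| 0–4 | oxygen | yes | yes |
| 5–10 | none | yes | yes |
| 5–10 | oxygen | no | yes |

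The complement of 'WHO 5–10 or oxygen on the form' is 'WHO 0–4 and none on the form'. With 'or' in (i), the two discordant rows fall on both sides.

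**Step 2: apply the rules to constructed records.** Eight profiles were run with assessments on Days 1–8, 15 and 31. Four rules were compared: WHO only; extended as written, with 'subsequent' meaning strictly later; extended with the event day also tested in (ii); and (i) requiring no oxygen in any source recorded that day. Entries are the event day.

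| Profile | WHO only | As written | Event day in (ii) | No oxygen in any recorded source |
|---|---|---|---|---|
| A. Both sources show oxygen throughout | none | none | none | none |
| B. WHO 5 throughout, form none throughout | none | 31 | none | none |
| C. WHO 5 throughout, form oxygen until Day 31, then none | none | 31 | none | none |
| D. Form oxygen whenever recorded, including Day 31; WHO 3 from Day 8 | 8 | 31 | none | none |
| E. WHO 5 to Day 5, form none from Day 5 | 6 | 5 | 6 | 6 |
| F. WHO 5 to Day 5, form none from Day 3 | 6 | 5 | 6 | 6 |
| G. WHO 5 to Day 8, form none from Day 8, next visit Day 15 | 15 | 8 | 15 | 15 |
| H. Both sources off from Day 5 | 5 | 5 | 5 | 5 |

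**Step 3: read the results.**
- In B, C and D the last visit is discordant. Nothing follows it, so (ii) is empty and the patient becomes a Day 31 event although one source records oxygen that day.
- In E, F and G the event falls on the last discordant day, one assessment before both sources are clear: 6 − 5 = 1 day in E and F, 15 − 8 = 7 days in G. Profile G assumes no assessment between Days 8 and 15, that is, discharge on Day 8.
- F shows that a longer discordant run does not lengthen the shift. Days 3 and 4 are rejected because (ii) sees WHO 5 afterwards.
- A and H, where the sources agree, give the same answer under every rule.
- The last two columns agree in all eight profiles.

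**The case against.** The strongest case against runs as follows.

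- **Neither source is named as the truth.** 'Too early' presumes that the source showing oxygen longest is right. In F the form alone gives Day 3, WHO alone Day 6, and the rule Day 5, between the two. In D the rule is later than the primary definition. This stands against calling every shift an error. It does not rescue the final visit, where the definition's own criterion (ii) treats either source as showing oxygen use and yet the patient is an event.
- **Some same-day disagreement is genuine weaning.** Listing 16.2.6.4 carries dated and timed changes in oxygen status. For the oxygen-therapy endpoint, section 7.6.2.3 takes the new status on a day of change. This stands, but that convention is not extended to the primary endpoint. The fix should use the last form status of the day.
- **'Subsequent' might include the event day.** Neither consequence then arises. That is not the ordinary meaning and the SAP does not say it. This reading also gives the same results as the fix, so it would still need to be written down.
- **It is one supportive analysis.** This is true, and it limits the weight of the point.

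A reader might infer that exchanging 'or' for 'and' in (i) settles the matter. It does not. The vital-signs schedule omits Day 15 although the WHO scale is scored then, so a paired form record is not guaranteed. Demanding a form entry would stop a patient with only a WHO score from qualifying at that visit.

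**Conclusion.** The defect is real and confined to discordant records in this supportive analysis. On such records the rule as written can date the event to a day on which one source still records oxygen. At a discordant last visit it makes the patient an event instead of a censored patient. The primary WHO-only analysis and all concordant records are unaffected.

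The date shift is one assessment interval: one day in hospital, longer after discharge. The effect on event counts or hazard ratios cannot be computed, because the SAP gives no discordance rate and the profiles are constructed. The conclusion assumes that 'subsequent' means strictly later and that the primary event-date and censoring rules carry over.

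Two stronger readings are not supported. A reader might infer that any patient on oxygen at every visit including Day 31 becomes an event; profile A shows no event when both sources record oxygen. A reader might also infer that the analysis is worthless for judging discordance. Criterion (ii) does use the form: it moves profile D from Day 8 to Day 31, and an oxygen entry after the last off-oxygen record makes the patient a non-event. The correction should be made because the rule misclassifies some of the inconsistent records it was added to handle.

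**What to change.** Restate criterion (i) as: no oxygen in any source recorded on that day, with at least one source recorded. That means WHO 0–4 where the scale is scored, and 'No supplemental oxygen needed' where the form is completed, using the last form status of the day. Equivalently, state that criterion (ii) includes the event day itself. Keep 'or' in criterion (ii). Say that patients with oxygen in either source at their last assessment are censored under the existing rule.

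Make the change in section 7.6.1, in the footnote of Table 14.2.1.1.5 and in the derivation behind Listing 16.2.6.11. The cost is a small change to wording and programming; no new data are needed.

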#### 7.6.2 Secondary Efficacy Analysis

Analysis of the key secondary and other time-to-event efficacy endpoints will be based on the ITT population. Other secondary efficacy endpoints will be based on the FAS population. A sensitivity analysis will be performed for the primary key secondary and other time-to-event efficacy endpoints in the FAS population. Descriptive statistics for all the secondary efficacy endpoints will be presented by treatment group and by study visit where appropriate. Data from all study visits, scheduled and unscheduled will be listed.

#### 7.6.2.1 Key Secondary Efficacy Endpoint

Time to sustained (ie, with no subsequent readmission to Day 31) hospital discharge (in days), defined as the first day, from randomisation through completion of the study, on which a patient

- i. discharges from the hospital, and
- ii. has no subsequent re-admission
Patients who reported sustained hospital discharge will be considered as an event on the date of discharge. Otherwise, in case of early study discontinuation due to any reason the patient will be censored at the date of the early study discontinuation. Otherwise, the patient will be censored at the date of the Day 31 visit or death date, whichever is first.

Time-to sustained hospital discharge (days) = (date of event or censoring – date of randomisation)

If date of event is the same as the randomisation date then time-to sustained hospital discharge will be considered as 1 day. If no data is available then time will be censored at time 0.

Time-to sustained hospital discharge will be analysed using the Kaplan-Meier method and 25th percentile, median and 75th percentile time will be presented by treatment group together with 95% CIs. The 95% CIs will be computed based on Brookmeyer-Crowley method and using a log log transformation. The mean time to hospital discharge and its standard error will be also presented by treatment group.

Time-to sustained hospital discharge between each dose of plitidepsin versus control arm will be compared using a stratified log-rank test, including the randomisation stratification factors as covariates, ie, Geographical Region (Europe vs. Rest of the World), Charlson Comorbidity index (0-1 vs. >1) and pre-baseline Barthel index ( $\geq$ 90 versus <90) as derived using the eCRF data. The 2-sided p-values for the comparison of each dose of plitidepsin versus control arm will be presented.

In the event that the primary efficacy endpoint of time to sustained withdrawal of oxygen supplementation is significant for both doses in the ITT population, the 2-sided p-values from the stratified log-rank test for the key secondary efficacy endpoint will be adjusted for multiplicity using the Hochberg step-up procedure to preserve the type 1 error rate in the comparison of each dose of plitidepsin versus control arm. This adjustment will not apply if the accrual in any of the experimental arms is stopped after the interim analysis.

For the key secondary efficacy endpoint, the Hochberg step-up procedure will be used to test the key secondary efficacy endpoint at the overall (2-sided) significance level as following:

- Let  $p_1 \le p_2$  denote the ordered unadjusted 2-sided p-values with associated null hypotheses  $H_{01}$  and  $H_{02}$ , where  $H_{0i}$  = time to sustained hospital discharge in plitidepsin [1.5 mg or 2.5 mg] arm = time to sustained hospital discharge in control arm.
- Then we follow the next stepwise procedure:
  - If  $p_2 \leq 0.05$ , reject  $H_{01}$  and  $H_{02}$  stop; else continue

- If  $p_1 \leq 0.05/2$ , reject  $H_{01}$  and stop
- Adjusted 2-sided p-values will be calculated as:
  - $\circ \quad q_2 = p_2$
  - $\circ q_1 = \min[2^* p_1, q_2]$

The adjusted 2-sided p-values for multiplicity using the Hochberg step-up procedure will be also presented.

As a supportive analyses, a stratified Cox proportional-hazards regression model, including the randomisation stratification factors as covariates, ie, Geographical Region (Europe vs. Rest of the World), and Charlson Comorbidity index (0-1 vs. >1) and pre-baseline Barthel index (≥90 versus <90) as derived using the eCRF data, will be applied to compare results between each dose of plitidepsin versus control arm. Hazard ratios, 95% CIs, and 2-sided p-values for the comparison of each dose of plitidepsin versus control arm will be presented.

The cumulative proportion of sustained hospital discharge (1-cumulative survival) will be displayed graphically by treatment group using a Kaplan-Meier curve. The key secondary efficacy analysis described above will be performed using the ITT population. A sensitivity analysis using the same model will be performed in the FAS population and a supportive analysis using the same models will be performed using the PP population.

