## **3.2 Key Secondary Efficacy Endpoint**

The key secondary efficacy endpoint is the time to sustained (ie, with no subsequent readmission to Day 31) hospital discharge (since randomisation).

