For the subset of patients with a pre-baseline (ie, in the prior month) Barthel Index  $\geq$  90, the percentage of patients who achieve complete recovery by Day 8 will be presented by treatment group and Clopper– Pearson 95% CI will be computed for the binomial proportion. In addition, the difference in the percentage of patients who achieve complete recovery by Day 8 between each dose of plitidepsin versus control arm will be presented for each dose of plitidepsin and the exact 95% CI will be computed for the difference in the percentage.

Complete recovery by Day 8 will be defined as

- i. meeting categories 0 to 2 on the 11-point WHO Clinical Progression Scale [at date of discharge when discharge is before or on Day 8 visit, or after the date of discharge but before or on Day 8 visit],
- ii. having Barthel index > 90/100 at time of discharge [when discharge is before or on Day 8 visit], and
- iii. with no readmission [or death] due to COVID-19 related signs or symptoms through Day 31

If discharge is after Day 8 visit then the patient will be considered as No complete recovery by Day 8.

If the 11-point WHO Clinical Progression Scale is missing or patient doesn't meet categories 0 to 2 between the date of discharge when discharge is before or on Day 8 visit and the Day 8 visit then the patient will be considered as **No complete recovery by Day 8**.

CONFIDENTIAL

If Barthel index at time of discharge is missing or  $\leq 90/100$  at time of discharge when discharge is before or on Day 8 visit then the patient will be considered as **No complete recovery by Day 8**.

If the 11-point WHO Clinical Progression Scale is between 0 and 2 and Barthel index is > 90 at time of discharge when discharge is before or on Day 8 however patient discontinues the study before Day 31, except due to death for any other reason than COVID-19 disease, then the patient will be considered as **No complete recovery by Day 8**.

The complete recovery by Day 8 rate between each dose of plitidepsin versus control arm will be analysed using a stratified logistic regression model. The model will be adjusted for the randomisation stratification factors, ie, Geographical Region (Europe vs. Rest of the World) and Charlson Comorbidity index (0-1 vs. >1) as derived using the eCRF data. The odds ratios, 95% CIs, and 2-sided p-values for the comparison of each dose of plitidepsin versus control arm will be presented.

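### Sustained hospital discharge is not voided by a later death: a patient discharged and then dead by Day 31 without readmission stays a favourable event

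*SAP*

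**What the plan says.** SAP 3.2 names the key secondary endpoint as "time to sustained (ie, with no subsequent readmission to Day 31) hospital discharge (since randomisation"; the bracket after *sustained* is its only qualification. SAP 7.6.2.1 gives two conditions: the patient is discharged, and the patient "has no subsequent re-admission". The event rule comes first: "Patients who reported sustained hospital discharge will be considered as an event on the date of discharge". Two censoring rules follow, each opening with *Otherwise*. One censors at early study discontinuation for any reason. The other reads: "Otherwise, the patient will be censored at the date of the Day 31 visit or death date, whichever is first". Tables 14.2.2.1.1, 14.2.2.2 and 14.2.2.3 in the shells and Table 14.2.4.2.1 in the addendum repeat the two conditions, and none adds survival.

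For the primary endpoint, SAP 7.6.1 requires that the patient "has no subsequent reutilisation of oxygen supplementation (5 to 10 on the 11-point WHO Clinical Progression Scale". On that scale 10 is dead (Appendix 4, footnote 13).

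SAP 7.8 defines complete recovery by Day 8 under protocol v6, for patients with a pre-baseline Barthel index of at least 90. Its third criterion is "with no readmission [or death] due to COVID-19 related signs or symptoms through Day 31". A patient who meets the WHO and Barthel criteria at a discharge by Day 8 is still a non-recovery if he or she "discontinues the study before Day 31, except due to death for any other reason than COVID-19 disease".

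**The concern.** A discharge followed by death at home is not a sustained recovery in any clinical sense, yet the written rule gives it full credit. The two main endpoints of one trial then treat the same later death in opposite ways. Elsewhere the SAP handles death as unfavourable: time to intensification of respiratory support counts death from any cause as an event, and a clinical status missing because of death is set to 10 (7.6.2.2 and 7.6.2.3).

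The trial is open-label, so the decision to discharge is made knowing the arm. If deaths at home differed between arms, this endpoint could not show it, and an arm could gain from early discharges that did not last. The endpoint is compared by stratified log-rank test and Cox model. It enters the Hochberg procedure when the primary is significant for both doses.

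**Working it through.** The SAP gives no sample size, power or death rate for this endpoint, so there is no figure to reproduce. The check applies the 7.6.2.1 rules, in their written order, to each kind of patient. The days are examples counted from randomisation.

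| Patient | Rule as written | With an alive-to-Day-31 condition |
|---|---|---|
| A: discharged Day 6, not readmitted, alive at Day 31 | Event, Day 6 | Event, Day 6 |
| B: discharged Day 6, not readmitted, dies at home Day 20 | Event, Day 6 | No event |
| C: discharged Day 10, not readmitted, alive at Day 31 | Event, Day 10 | Event, Day 10 |
| D: discharged, readmitted, dies | Censored | No event |
| E: dies in hospital | Censored | No event |

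B meets both conditions, so neither *Otherwise* rule is reached. B is scored the same as A and ahead of C. Only deaths like D and E reach the censoring rules.

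Under 7.6.1, if patient B had come off oxygen on Day 5, the death on Day 20 (WHO 10, inside the range 5 to 10) would cancel that event and B would be censored. This reading takes a score of 10 as assigned at death.

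**What the rule cannot see (assumed inputs, not an estimate for this trial).** Assume exponential discharge times with the same 8-day median in both arms. That is the control median for oxygen withdrawal in SAP 2.3, borrowed here. Let q be the share of discharged patients who die without readmission by Day 31, and hold those patients as non-events at Day 31.

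- λ = ln 2 / 8 = 0.0866 per day
- P = 1 − exp(−31λ) = 0.932
- P/λ = 10.76 days
- Event rate = (1 − q)P / [(1 − q)P/λ + 31q]
- q = 0: 0.0866; q = 1%: 0.9225/10.957 = 0.0842; q = 3%: 0.9038/11.362 = 0.0795; q = 5%: 0.8852/11.767 = 0.0752

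Ratios, plitidepsin to control:

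- 1% in both arms: 1.00
- 3% against 1%: 0.0795/0.0842 = 0.94
- 3% against 0%: 0.0795/0.0866 = 0.92
- 5% against 0%: 0.0752/0.0866 = 0.87

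Under the SAP rule the ratio is 1.00 in every case, because these deaths leave the event flag and its date unchanged.

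**Protocol v6 endpoint, same exercise.** For a patient who already met the WHO 0 to 2 and Barthel >90 criteria with discharge by the Day 8 visit:

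- a later COVID-19 death is a non-recovery;
- leaving the study alive before Day 31 is a non-recovery;
- a later death from another cause remains a recovery.

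A patient not discharged by the Day 8 visit is a non-recovery whatever follows.

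**The case against.** *The deaths are reported elsewhere.* Overall survival is compared in the ITT population, mortality is given at Days 4, 8, 15 and 31, and deaths are tabulated and listed. So they are not hidden from the reader. That does not correct how this endpoint scores them.

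*Death is a study discontinuation, and Listing 16.2.6.6 shows a death as censored.* Both fit patients D and E. Neither cancels an event already assigned.

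*The SAP may be faithful to the protocol.* It was written from protocol v7, which is not shown. If that protocol defines the endpoint in the same words, the change is to the endpoint and not a correction of transcription. This stands, and it is a reason to label the analysis.

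*Formal testing is conditional.* The Hochberg adjustment applies only if the primary is significant for both doses. This also stands, although the unadjusted p-values and hazard ratios are reported regardless.

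*The effect may be negligible.* Recruitment stopped before 33% of events. At the planned ratio, 175 events correspond to 175 × 609/530 = 201 patients, or about 67 per arm (an assumption). With 2 × 67 × 0.932 = 125 events in a pair, the standard error of the log hazard ratio is about 2/√125 = 0.18. The 3%-against-0% case gives ln 0.92 = −0.083, less than half of that. This stands as to size, not as to definition.

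A reader might infer that death is scored as the best outcome. It is not: patient B ranks with other Day 6 discharges, and earlier discharges still rank higher. Nor can each such death be priced in percentage points of success, since the analysis is a log-rank test and not a comparison of proportions.

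**Conclusion.** The inconsistency is real on the SAP's wording. A patient discharged and then dead by Day 31 without readmission is a favourable event in the key secondary analysis, while a later death voids the primary event. No other section repairs it. No magnitude can be stated, because the number of such deaths is not given and may be small; the ratios shown describe the rules, not the trial. The conclusion rests on the SAP alone, without the protocol.

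A reader might go further and infer that the v6 endpoint generally counts non-COVID deaths as complete recovery, and that this too is an error. The SAP does not support that. The exception is explicit, belongs to an exploratory analysis that regulators requested, and covers only patients with a pre-baseline Barthel index of at least 90 who already met the WHO 0 to 2 and Barthel >90 criteria with discharge by the Day 8 visit. A sensitivity line is enough there.

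**What to change.** In 3.2 and 7.6.2.1, and wherever the shells and addendum repeat it, define the event as discharge alive with no readmission and no death from any cause through Day 31, dated at discharge.

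In the same place, state one rule for all deaths without a sustained discharge, in hospital or after it: for example, all as competing events, or all as non-events held at Day 31. Holding only the post-discharge deaths at Day 31 while in-hospital deaths stay censored at the death date would replace one inconsistency with another.

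SAP version 4.0 is dated 21 April 2023 and the database locked on 26 April 2023. Report the result as a labelled post-lock analysis beside the prespecified definition, with the number of affected patients per arm. For Table 14.2.1.4, keep the v6 definition and add one sensitivity line counting any death through Day 31 as non-recovery.

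The cost is one clause, one rule for deaths, a changed event flag and reruns of the discharge tables and figures. Death dates are already collected and listed.
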